8.3 Cardiometabolic Risk

To evaluate exploratory outcomes, cardiometabolic risk factors will be assessed at screening, randomization (week 0) and week 24. Fasting blood samples (i.e., following an overnight fast of at least 8 hours) will be drawn on each occasion and assayed for a CMP and lipid panel. (Samples will be analyzed by Quest Diagnostics.) Responders who are not randomized will not complete the CMP and lipid panel at randomization (week 0). All participants will complete these analyses at screening and at week 24.

Blood pressure and pulse will be measured on each occasion using an automated monitor (Dinamap, model 9300). Two readings will be taken on each occasion (at 1-minute intervals), after subjects have been seated for at least 5 minutes. Waist circumference (measured horizontally halfway between the lowest rib and the top of the hipbone) to the nearest 0.1 cm will be assessed on the same schedule. Two waist measurements will be obtained at each assessment visit.

8.4 Questionnaire Measures

Eating characteristics. Self-report measures of hunger, impulsivity, and the relative reinforcing value of food will be administered to all subjects at all three outcome assessments. The Eating Inventory (EI – hunger subscale ⁹⁰) and one-week VAS ratings will be used to assess hunger. RRV_{food} will be assessed by the Power of Food Scale (PFS ⁹¹) and general sensitivity to reward will be assessed by the Behavioral Inhibition/Activation Scale (BIS/BAS).⁹² The Barratt Impulsiveness Scale (BIS-15)⁹³ will be used to assess impulsivity. We will also collect measures of additional eating characteristics for use in exploratory analyses, including past-week VAS appetite ratings ⁹⁴, cognitive restraint (EI), disinhibition (EI), and binge eating (Questionnaire on Eating and Weight Patterns [QEWP-5]⁹⁵). Craving frequency will be assessed using the Food Craving Questionnaire – Trait – reduced (FCQ-Tr)⁹⁶ and emotional eating using the Dutch Eating Behavior Questionnaire (DEBQ)⁹⁷ Emotional Eating subscale. Perceived barriers to health behavior change ⁹⁸, diet and exercise self-efficacy (i.e., Weight Efficacy Life-Style Questionnaire [WEL]⁹⁹, SCI Exercise Self Efficacy Scale [ESES]¹⁰⁰), social support for healthy eating and physical activity (i.e., Ball and Crawford Social Support Scale)¹⁰¹, will also be assessed. Reinforcing efficacy of high- and low-energy density snack foods and active and non-active activities will be assessed using a computerized questionnaire during the in-person assessment.¹¹⁴ Food addiction will be assessed using the Yale Food Addiction Scale (YFAS).¹¹⁵

The Highly Processed Food Withdrawal Scale (ProWS)¹¹⁶ will be administered on a separate timeline from the questionnaires described above. Participants will first complete the ProWS at their screening visit (week -5) and will be sent an email every other day with a link to complete this questionnaire until the second intervention visit (week -2). This timeline will allow us to assess indicators of withdrawal that may develop early in treatment when an individual attempts to cut down on highly processed foods.

Psychosocial characteristics. Psychosocial characteristics will be assessed on the same schedule as the primary outcomes. Mood will be assessed using the PHQ-9¹⁰² and the C-SSRS⁸⁶. Perceived stress will be assessed using the Perceived Stress Scale (PSS)¹⁰³ and anxiety using the GAD-7. Quality of life will be assessed using SF-36.¹⁰⁴ The Philadelphia Mindfulness Scale (PHLMS) will be used to assess general mindfulness and acceptance.¹¹⁷ Physical activity will be assessed by the Paffenbarger Physical Activity Survey.¹⁰⁵ A brief questionnaire will assess hours of sleep per week.¹¹⁸

9 Statistical Plan

9.1 Sample Size and Power Determination

A total sample size of 150 subjects will provide at least 80% power to detect all three primary outcomes. All power analyses were conducted using G*Power 3.1 at an alpha of .05. A correction for multiple comparisons is not proposed due to the preliminary nature of this research.

Phase 1: For the co-primary outcome - percent weight loss at the end of the BT run-in as predicted by baseline satiety, postprandial GLP-1, and gastric emptying - an estimated effect size for each predictor of

$\rho^2 = .042$ was selected as the lower estimate from studies predicting weight loss from VAS satiety ratings and GLP-1 (ρ 's $\geq .20$).^{16, 106} (We did not find studies using gastric emptying to predict weight loss, and the effect sizes for comparisons between BMI categories of $\rho^2 = .07 - .30$ were less conservative.^{43, 78}) Based on this estimate, a sample size of 150 subjects would yield 80% power to detect statistical significance for the three individual predictor variables. The second co-primary outcome - non-responder status as predicted by these three predictors in discriminant analysis - would have 90.1% power with this sample size, based on power analysis for a 2-group MANOVA for 3 response variables^{107, 108} with an estimated combined effect size of $\rho^2 = .10$.

Phase 2: For the primary outcome - percent weight change from randomization to week 24 among early non-responders - estimated group means, variances, and attrition rates were derived from data from prior studies conducted at our Center and from previous research in early non-response to BT e.g.,⁴. The estimated treatment effect is based on the placebo-subtracted effect of 28 weeks of phentermine 15.0 mg of 4.5 kg (4.4% of initial weight), as determined by a multi-arm RCT that enrolled 219 total patients in the placebo and phentermine 15.0 mg groups.⁷⁷ We selected this result as the basis of our power analysis because it most closely matched the phentermine dose and duration used in the present study. Other previous RCTs examining the effect of phentermine monotherapy have typically administered a 30.0 mg dose for 12 to 16 weeks. The majority of these trials have achieved larger placebo-subtracted weight losses of 5.4 to 7.8 kg.^{72, 74-76} (One randomized trial reported a 4.0 kg placebo-subtracted loss with a different formulation, phentermine resin 30.0 mg,⁷³ and one reported a 3.3% placebo-subtracted loss when both phentermine 37.5 mg and placebo were combined with a 900-1100 kcal/day meal replacement diet, resulting in large mean weight losses in both groups.¹⁰⁹) An additional study suggested that the difference in mean weight loss between phentermine 15.0 mg and phentermine 30.0 mg (both when combined with lorcaserin) is small (0.6 kg mean difference).¹¹⁰ We therefore believe that participants provided with 24 weeks of phentermine 15.0 mg are likely to achieve a placebo subtracted loss of $\geq 4.5\%$ of initial weight. (Most early phentermine studies reported results in kg, which is roughly equivalent to percent weight loss in populations with obesity.)

We predict a 24-week post-randomization weight loss among early non-responders of 6.5% in BT+M and 2.0% in BT+P, with expected standard deviations of 5.5%. We expect 33% of the initial baseline sample of 150 subjects to be categorized as early non-responders following the BT run-in.^{4, 7, 8} Based on these estimates, a randomized sample size of 50 non-responders (25 per group), assuming a 20% attrition rate, will give us 81.5% power to detect between-treatment group differences at week 24 of 4.5% (effect size: $d = 0.82$).

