9.2 Statistical Methods

Data quality and integrity will be checked by assessing the data for missing and out-of-range values and univariate normality with basic statistical procedures, including descriptive statistics and visual graphical displays (e.g., histograms, scatter plots). All questions of data quality and integrity will be investigated before any statistical modeling is conducted. To test the adequacy of randomization, preliminary analyses will include a comparison of demographic and baseline characteristics between randomized treatment groups (BT+P and BT+M; t-tests or Wilcoxon rank sum tests for continuous variables and Chi-Square test or Fisher's Exact test for categorical data). If baseline imbalances are observed, the relevant variables will be included as covariates in analyses relevant to those outcomes.

All analyses will be conducted using the ITT principle. Analyses will be two-tailed with an alpha of 0.05, and will be conducted using SPSS version 24.0 or SAS version 9.4. For all analyses, residual analyses will be conducted to check for outliers, influential points, and violations in the normality assumption. If violations are detected, variance-stabilizing transformations will be considered.

Phase 1: Analyses will be based on the initial population of subjects who attend at least one post-baseline treatment visit during the BT run-in. Multiple regression will be used to evaluate predictors of early weight loss with BT (% loss at week 0) and discriminant analysis will be used to assess which variables predict categorization as a non-responder (who has lost $< 2\%$ of initial weight at week 0). The primary analyses will test the hypothesis that the set of baseline satiety measures (VAS satiety ratings, postprandial changes in GLP-1, and gastric emptying) predict these outcomes when considered simultaneously. Additional analyses will evaluate demographic characteristics, secondary predictor variables (fasting hunger, RRV_{food}, reinforcing efficacy of food, impulsivity, fasting ghrelin, fasting leptin, and lower postprandial changes in insulin and PYY), and exploratory variables as predictors of early weight loss.

Factor analysis will be used to assess whether predictor variables cluster into phenotypes.

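### The 80% power stated for the individual Phase 1 predictors at N = 150 matches a one-tailed test; under the planned two-tailed test it is about 70–72%, before any run-in losses.

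*Combined protocol and SAP*

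**What the plan says.** Section 9.1 opens by promising at least 80% power for all three primary outcomes with 150 subjects, and adds: "All power analyses were conducted using G*Power 3.1 at an alpha of .05". For the first Phase 1 co-primary outcome it takes a squared correlation of .042 for each of baseline satiety, postprandial GLP-1 and gastric emptying, drawn from published correlations of .20 or more. It concludes that "a sample size of 150 subjects would yield 80% power to detect statistical significance for the three individual predictor variables". The number of tails is not stated there, and no multiplicity adjustment is made ("A correction for multiple comparisons is not proposed due to the preliminary nature of this research").

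Section 9.2 says of the analyses in general: "Analyses will be two-tailed with an alpha of 0.05". It makes no exception for Phase 1, where the method is multiple regression on percent loss at week 0. The Phase 1 population is defined by attendance: "Analyses will be based on the initial population of subjects who attend at least one post-baseline treatment visit during the BT run-in". Section 4.6 ends recruitment at 150 enrolled. Under section 7.5, a subject who does not attend the randomization visit within 2 weeks of the end of the run-in cannot continue in the study.

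**The concern.** The power figure and the test appear to belong to different analyses. A squared correlation near .04 with 150 subjects is a familiar case: it gives about 80% power one-tailed and about 70% two-tailed. If the figure was computed one-tailed, the claim in section 9.1 does not describe the test in section 9.2.

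The outcome is one of the two Phase 1 co-primaries (sections 2.1 and 3.3.1). If true power is 70–72%, the chance of missing a given predictor at the planned effect is 28–30%, not 20%. A reader relying on section 9.1 would then give a non-significant satiety, GLP-1 or gastric-emptying coefficient more weight as evidence of no association than it deserves.

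A second, smaller issue pushes the same way. The calculation uses everyone enrolled, but the outcome exists only for those weighed at week 0.

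**Working it through.** **Inputs.** From section 9.1: N = 150, squared correlation .042 per predictor, source correlations of at least .20, alpha .05. From section 9.2: two-tailed tests and a multiple regression with three primary predictors.

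**Formula.** Power for one coefficient in a fixed-predictor regression uses the noncentral t distribution, with df = N − 3 − 1 = 146 and noncentrality δ = √(f² × N). The critical t is 1.655 one-tailed and 1.976 two-tailed.

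**Effect size.** Section 9.1 leaves some room in how .042 becomes f², so four readings were tried:

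- .042 entered directly as f²: δ = √(.042 × 150) = 2.510
- f² = .042/(1 − .042) = .0438: δ = 2.564
- correlation of exactly .20, f² = .04/.96 = .0417: δ = 2.500
- three uncorrelated predictors, each uniquely explaining .042, so residual variance is 1 − 3 × .042 = .874 and f² = .042/.874 = .0481: δ = 2.685

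**Results at N = 150.**

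| f² | Power, one-tailed | Power, two-tailed | N for 80%, one-tailed | N for 80%, two-tailed |
|---|---|---|---|---|
| .0420 | 80.3% | 70.3% | 149 | 189 |
| .0438 | 81.8% | 72.2% | 143 | 181 |
| .0417 | 80.0% | 70.0% | 150 | 191 |
| .0481 | 84.8% | 76.0% | 131 | 166 |

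The plan's 80% at N = 150 is reproduced one-tailed by the first and third rows, where the required N is 149 or 150. No two-tailed row comes within 2 points of 80%. A Fisher z approximation with a correlation of .205 gives 71.2% two-tailed, in line with the table.

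**Detectable effect.** Setting two-tailed power to 80% at N = 150 gives f² = .0530. The squared correlation is then .0530/1.0530 = .050, a correlation of about .22.

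**Run-in losses.** The documents give no rate of missing week 0 weights; the 20% attrition in section 9.1 belongs to the randomized phase. Taking loss as an assumption, with f² from .042 to .0438 and two-tailed tests:

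| Assumed loss | N with week 0 weight | Power |
|---|---|---|
| 5% | 142 | 67.9–69.8% |
| 10% | 135 | 65.7–67.5% |
| 20% | 120 | 60.5–62.4% |

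**The case against.** The strongest counter-argument is that section 9.2 frames the primary Phase 1 hypothesis around the three satiety measures as a set, considered together. The natural test of a set is the 3-df F test, and that test is well powered. With the combined effect of .10 that section 9.1 uses for the discriminant analysis (borrowed here as an assumption), power at N = 150 is 93.7%, and still 86.8% at N = 120. With R² = .126 at N = 150 it is about 98%. This stands as far as it goes: the shortfall affects the individual coefficients, not a set-level test. But section 9.1 makes its claim for the individual predictors, and the set-level test does not yield the stated 80% either.

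A second objection is that 70–72% leaves out the 76.0% reading. That reading is possible, but it needs the three predictors to be uncorrelated. Section 1.1.3 describes gastric emptying and several neuropeptides as influencing one another, which makes it hard to assume. It also falls short of 80%.

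Third, the tails used in the software are inferred from the match, because section 9.1 does not state them. That is fair. The conclusion does not depend on it: whichever option was chosen, the planned two-tailed test does not have 80% power on any of these readings. The directional hypotheses in section 2.1 could support one-tailed tests, but section 9.2 does not specify them.

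Finally, the amount of run-in loss is unknown. Only its direction follows from the documents.

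**Conclusion.** The concern holds. At two-tailed alpha .05 and N = 150, power for each individual predictor is about 70–72% under the usual conversions of .042, against the stated 80%: an overstatement of 8 to 10 points. On the most favourable reading it is 76.0%, still 4 points short. The stated 80% is matched by a one-tailed calculation. The opening promise of at least 80% power for every primary outcome therefore fails for this one.

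The result rests on the plan's own effect size, N and alpha, and on a three-predictor regression. Any missing week 0 weights lower power further, by an amount the plan does not let one fix; at an assumed 10% loss it is 66–68%. The finding does not extend to a set-level test of the three predictors.

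**What to change.** In section 9.1:

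1. State the number of tails used, and whether .042 is a squared correlation or f².
2. Replace the Phase 1 figure: at two-tailed alpha .05, 150 subjects give about 70–72% power per predictor for a squared correlation of .042 (76% if the predictors are taken as uncorrelated), or 80% power for a squared correlation of about .05.
3. Give the same figure for the number expected to have a week 0 weight, with the assumed loss rate stated.
4. Remove the claim of at least 80% power for this outcome.

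If one-tailed tests were intended for Phase 1, section 9.2 would have to say so and justify it. Reaching 80% two-tailed instead would take about 181 to 191 subjects with a week 0 weight, but the correction does not require this.

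The cost is wording and a less favourable stated figure. Enrolment, endpoints and analyses are unchanged.

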- Phase 2: To test the effect of augmenting BT with the weight loss medication phentermine 15.0 mg (BT+M), compared to BT plus placebo (BT+P), on weight loss in early non-responders who lose < 2.0% of initial weight during a 4-week behavioral run-in. Percent weight loss from randomization to week 24 is the study's primary endpoint.

Secondary:

- Phase 1: To examine whether additional behavioral characteristics (higher fasting hunger, relative reinforcing value of food [RRV_{food}], and impulsivity) and neuropeptides (higher fasting ghrelin, lower fasting leptin, and lower postprandial changes in cholecystokinin and peptide YY) predict 4-week weight loss, as well as categorization as a non-responder during the BT run-in.
- To compare the portion of early non-responders who achieve a post-randomization loss of $\geq 5\%$ and $\geq 10\%$ of initial body weight with BT+M and BT+P.
- To compare non-responders treated with BT+M vs. BT+P in changes in hunger, satiety, RRV_{food}, and impulsivity between randomization and week 24.
- To explore differences in percent weight loss from randomization to week 24 between early non-responders treated with BT+M and early responders treated with BT alone.

Number of Subjects

150 subjects (180 in-person screenings to obtain 150)
60 subjects randomized to study medication(s)

**Main Inclusion and
Exclusion Criteria**

Key Inclusion Criteria

1. BMI $\geq 31 \text{ kg/m}^2$ (or 28 kg/m^2 with obesity-related comorbidity)
2. Age ≥ 21 years and ≤ 70 years
3. Has a primary care provider (PCP) responsible for providing routine care
4. Plans to remain in the Philadelphia area for the next 9 months or more

Key Exclusion Criteria

5. Pregnant or nursing, or plans to become pregnant in the next 9 months.
6. Uncontrolled hypertension (systolic blood pressure $\geq 140 \text{ mm Hg}$ or diastolic blood pressure $\geq 90 \text{ mm Hg}$)
7. Type 1 diabetes
8. Type 2 diabetes
9. A fasting blood glucose $> 126 \text{ mg/dL}$ (on second assessment after first elevated value, patients are excluded if they have both fasting blood glucose $> 126 \text{ mg/dL}$ and HbA1c ≥ 6.5)
10. History of cardiovascular disease (e.g., coronary artery disease, stroke, arrhythmias, congestive heart failure, or heart block greater than first degree)
11. Clinically significant hepatic or renal disease
12. Hyperthyroidism
13. Other thyroid disease, not controlled.
14. History of malignancy (except for non-melanoma skin cancer) in past 5 years

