4.6 Total Number of Subjects and Sites

Recruitment will end when 150 subjects are enrolled. It is expected that approximately 50 of these subjects (33%) will become classified as early non-responders to BT and enrolled in the randomized trial.

4.7 Vulnerable Populations:

Children, pregnant women, fetuses, neonates, or prisoners are not included in this research study.

5 Study Interventions

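### The Phase 2 power of 81.5% does not follow from the plan's own inputs: with a two-tailed 0.05 test and 20% attrition it is about 71%

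*Combined protocol and SAP*

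**What the plan says.** Section 9.1 (Phase 2) predicts a 24-week post-randomization loss of "6.5% in BT+M and 2.0% in BT+P", "with expected standard deviations of 5.5" percent, and concludes that "a randomized sample size of 50 non-responders (25 per group), assuming a 20% attrition rate, will give us 81.5% power" for a 4.5-point difference, printed as d = 0.82.

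The same section opens with the software and significance level: "All power analyses were conducted using G*Power 3.1 at an alpha of .05". It does not name the test or say whether it is one- or two-tailed. It also makes an overall claim: "A total sample size of 150 subjects will provide at least 80% power to detect all three primary outcomes".

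Section 9.2 settles sidedness for the analysis: "Analyses will be two-tailed with an alpha of 0.05".

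On the number randomised, section 4.6 expects that "approximately 50 of these subjects (33%) will become classified as early non-responders to BT and enrolled in the randomized trial", which agrees with section 9.1. The Study Summary (Number of Subjects) gives 60.

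**The concern.** The power statement gives every input needed to check it: the randomised number, the attrition, the means, the SD and alpha. A standardised difference of 0.82 with about 20 evaluable subjects per arm is too little for 80% power in a two-tailed test, so a figure above 81% after 20% attrition does not look right.

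This is the power for the study's primary endpoint. If it is overstated, the trial is more likely than its readers think to miss the effect it was designed around. A non-significant result judged against a claimed 81.5% would then count for more than it should as evidence that medication does not help early non-responders. The statement that all three primary outcomes have at least 80% power depends on the same figure.

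**Working it through.** **Inputs**

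- Randomised: 50, 25 per arm (section 9.1), allocated 1:1 (section 3.2).
- Attrition: 20% (section 9.1). Read as no week-24 weight, this leaves 25 × 0.80 = 20 per arm.
- Difference: 6.5 − 2.0 = 4.5 points; SD 5.5 (section 9.1). d = 4.5/5.5 = 0.818, printed as 0.82.
- Test: two-tailed, alpha 0.05 (section 9.2).

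**Formula.** For a two-sample t-test with n per arm, the noncentrality parameter is δ = d·√(n/2) on 2n − 2 degrees of freedom. Two-tailed power is P(|T| > t₀.₉₇₅), and one-tailed power is P(T > t₀.₉₅), where T is noncentral t with parameter δ.

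**Looking for the plan's 81.5%**

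| Setting | n per arm | Power |
|---|---|---|
| One-tailed, 20% attrition | 20 | **81.49%** |
| Two-tailed, no attrition | 25 | 80.9% (81.1% with d = 0.82) |
| One-tailed, no attrition | 25 | 88.6% |
| Two-tailed, attrition taken as 25/1.2 | 20.8 | 73.1% |

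The first row matches the printed figure to its last decimal. The second is close but not equal. Neither satisfies both conditions the plan sets: the first breaks the two-tailed rule of section 9.2, and the second drops the attrition that the sentence says is included.

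**The plan's own conditions.** With n = 20, δ = 0.818 × √10 = 2.587 on 38 degrees of freedom, and the two-tailed critical value is 2.024. Power is **71.3%** (71.5% with d rounded to 0.82; 73.5% by the normal approximation).

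**Size of the shortfall**

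- 81.5 − 71.3 = 10.2 percentage points. The type II error is 28.7% instead of 18.5%.
- With 20 per arm, 80% two-tailed power needs d = 0.909, that is 0.909 × 5.5 = 5.0 points.
- At the 4.4% placebo-subtracted effect that section 9.1 takes from its source trial, d = 4.4/5.5 = 0.80 and power is 69.3%.
- With the Summary's 60 randomised, 30 × 0.80 = 24 per arm gives 79.2%.
- Two-tailed 80% power at a 4.5-point difference needs 25 evaluable per arm (80.9%). That is 50/0.80 = 62.5, so 63 randomised, or 64 in equal arms.

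**The case against.** The strongest reply is that the planned analysis is not a completers-only t-test. Section 9.2 specifies a mixed effects model on all randomised subjects, and section 9.2.1 uses all available data under missing at random. Covariates may enter if baseline imbalances are seen, and section 8.1 has weight taken at every clinic visit. Such a model could have more power. As an illustration with correlations that are not in the documents, a covariate correlated with the outcome at r = 0.3 would raise power at 20 per arm to about 75%, and at r = 0.5 to about 83%. About 0.44 would be needed for 80%, and about 0.47 for 81.5%.

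This limits what can be said about the power of the final model, but it does not support the printed figure. Section 9.1 states no correlation, covariate or variance reduction, and its d is the raw difference divided by the raw SD. Section 8.1 also restricts the primary-outcome weights to the assessment visits, so a gain from interim weights cannot be presumed.

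Three smaller points:

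- That a one-tailed setting was used is an inference from the exact match. The documents do not say so, and the conclusion does not need it.
- Section 9.1 does not define attrition, and section 7.5 invites subjects who have stopped treatment to the week-24 visit. Missing week-24 weight is still the natural meaning in a power statement, and even with no loss the two-tailed result is 80.9 to 81.1%.
- Section 9.1 argues for an effect of at least 4.5%, mostly from larger effects in other trials. That bears on whether 4.5 is cautious, not on the power at 4.5. The same section justifies omitting a multiplicity correction by the preliminary nature of the work; it gives no such reason for a one-tailed test.

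**Conclusion.** The stated power is wrong on the plan's own terms. For the unadjusted two-group comparison behind d = 0.82, with 20 evaluable per arm and a two-tailed 0.05 test, power is 71.3%, about 10 points below the stated 81.5%. The claim of at least 80% power for all three primary outcomes therefore does not hold for Phase 2. The two Phase 1 figures were not part of this check.

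The result rests on reading attrition as a missing week-24 weight and on taking no credit for precision gains that the plan does not state. The conflict between 50 and 60 randomised is a separate inconsistency. It does not explain the figure, because 60 gives 79.2%.

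**What to change.** Rewrite the Phase 2 power statement in section 9.1 along these lines: 50 randomised, 20% without a week-24 weight, 20 per arm evaluable, two-sample t-test, two-tailed alpha 0.05, difference 4.5 points, SD 5.5 (d = 0.82), power about 71%; 80% power for a difference of about 5.0 points. Remove the claim that all three primary outcomes have at least 80% power, or limit it to the outcomes for which it is shown.

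Use one randomised number in the Study Summary, section 4.6 and section 9.1, and quote the power for that number (about 71% at 50, about 79% at 60).

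If the sponsor relies on a gain from the mixed model or from covariates, section 9.1 should name the model and state and justify the assumed correlation.

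The cost is wording only. No subjects, procedures or analyses change, but the stated power becomes less favourable. Keeping 80% at a 4.5-point difference by enlarging the trial would mean randomising 63 or 64, which this correction does not require.
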